#### Device Description:

The EUM300 is composed of three units: Disposable electrode, Maternal unit and Interface unit.

Disposable electrode applied part – Proprietary bio-compatible patch electrode array with nine Ag/AgCl and hydrogel connections. Electrode is made by US based manufacturers: Lead-Lok, Sandpoint, ID and Molex, Naperville, IL.

Maternal Unit – The maternal unit is connected via a proprietary connector to the electrode. The EMG signals are amplified by an analog front-end. OB-Tools Algorithm runs on a DSP board and the result – Fetal Heart Rate and Uterine Activity are transmitted via Bluetooth. The unit contains a 4.2V Li-Ion rechargeable battery. The battery allows 24h of work and must be charged away from the patient.

Interface unit – Wall mount unit translates the information received from a paired Bluetooth Maternal unit. In this setup the EUM is used as a secondary system, one that

Version 5.13; June 19, 2020

is not involved with clinical decisions. In this case a PC computer receives the bluetooth transmission from the maternal unit and saves it into an Excel readable file. A primary monitor that is used for clinical decisions may also be connected to the PC and its data is recorded into the same file for comparison. The file format is a simple 6 column format: Date, Time, EUM UA, EUM FHR, Monitor UA, Monitor FHR. The file can be read and analyzed using Excel, Matlab and other statistical tools.

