**Statistics:**

Routine parametric and non parametric statistical analysis will be performed. Given that each patient serves as her own control (since we will be comparing the EUM device to the routinely used devices simultaneously), we will be able to limit the number of women enrolled.

To assess the improvement in continuity of readings in EUM, continuity in readings will be compared between EUM, Doppler, and FSE from the same patients. Assuming the number of minutes of unreadable tracing for the EUM is less than the Doppler by one minute, the standard deviation of difference in minutes by the two devices is three minutes, and there are two obstetrician readings per subject, to reach a power of 80% with 0.05 significance level, 39 patients will be needed for our primary outcome as listed below.

Regarding assessment of contractions, continuity in readings will be compared between EUM and IUPC in the same patients. To assess the improvement in continuity of readings in EUM, continuity in readings (yes or no) will be compared between EUM and

Version 5.13; June 19, 2020

IUPC from the same patients. A McNemar test will be used to compare the proportion of continuity between these two methods. With N=55 patients, the study will have at least 80% to detect an odds ratio of 3.2 associated with continuity between EUM and IUPC with a two-sided type I error rate of not more than 5%, assuming 50% of discordant pairs. It is acknowledged that the study has only adequate power to detect a substantial difference between EUM and Doppler, and between EUM and IUPC however, anything below this level would be of less clinical interest and the result we obtain from this study will be used to design more definitive studies in the future. Thus, the number of patients required to address each of the aims of the study is as below:

1. Fetal heart rate monitoring: EUM device v. external monitor v. FSE n = 39
2. Contraction monitoring: EUM device v. external monitor n = 55 obese and n = 55 nonobese subjects; EUM device v. intrauterine pressure catheter n = 55 obese and n = 55 nonobese subjects.
3. Productive v. non-productive contractions: EUM device v. external monitor n = 55 subjects.

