Because many of these patients will overlap due to the fact that they will serve as their own control and will be monitored simultaneously for fetal heart rate and change in cervical exam, it is anticipated that the maximum number of patients required in this study will not be more than 220 patients since 55 obese and 55 non-obese patients will be needed and additional patients may be needed to evaluate productive contractions. In addition to comparing the continuity in readings, in assessing contractions, we will also compare average frequency of contractions, the duration of contraction, maximum height of the contraction, the total Montevideo units obtained, the timing of the contraction and the amount of discontinuous tracings from the devices. In assessing fetal heart rate, we will compare average fetal heart rate, baseline heart rate, the number accelerations, the number of decelerations, the timing of the accelerations, the timing of decelerations, the maximum fetal heart rate achieved during acceleration, the lowest fetal heart rate achieved during deceleration, and compare the degree of variability in the tracing. A continuous outcome will be compared using a paired t-test.

Version 5.13; June 19, 2020

As each patient is serving as its own control, missing data is unlikely to be an issue in this study once the patient consents. If the monitoring is less than 30 minutes, these patients will not be used in analysis due to concern for completeness and accuracy.

Safety assessment:

Safety and tolerability will be assessed by recording of adverse events. Adverse events will be reported. Adverse events will be assessed in terms of their seriousness, severity, and relationship to the study device. To date more than 800 patients have used the device in clinical trials and there have been no safety events reported with the use of the device to date.

Potential benefits:

There is no immediate benefit to the subject from her participation in this study. The study results will support the development of the EUM300pro system, which may have clinical importance in providing the care provider with more continuous and accurate monitoring of fetal heart rate and contractions in a less invasive way. These parameters will aid the medical staff in making timely clinical decisions and increasing the chances of attaining a successful treatment and/or delivery.

Potential risks:

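### The 39 women set for the fetal heart rate primary give 80% power only if the two readers are nearly uncorrelated, and the plan does not say that heart rate recordings from the other enrolled women will be used

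*Combined protocol and SAP*

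**What the plan says.** Continuity of the fetal heart rate reading, in unreadable minutes out of 30, is one of two primary outcomes. The Statistics section sizes it on a one-minute advantage of EUM over Doppler and an SD of 3 minutes for the paired difference, and it counts on a second look at each tracing: "there are two obstetrician readings per subject". On these inputs its target is 39 women, for 80% power at the 0.05 level. Materials and Methods repeats the calculation. The list of numbers by aim gives "Fetal heart rate monitoring: EUM device v. external monitor v. FSE n = 39". For contractions it gives 55 obese and 55 nonobese women for each comparison, and the text below it caps enrolment at 220.

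The same section expects many women to count towards several aims, since they "will be monitored simultaneously for fetal heart rate and change in cervical exam". Materials and Methods has both the EUM and the clinical monitor data captured on the study laptop. Device Description adds: "The file format is a simple 6 column format: Date, Time, EUM UA, EUM FHR, Monitor UA, Monitor FHR". The clinical monitor is external or internal according to clinical need. The only stated exclusion from analysis is monitoring shorter than 30 minutes.

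**The concern.** Two gaps meet on one primary outcome.

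First, the 39 counts on a gain in precision from a second reading. How large that gain is depends on how closely two obstetricians agree about the same tracing. The plan neither states nor justifies a correlation. Two people reading one tracing would ordinarily be expected to agree to a fair degree, and in that case the second reading adds little and 39 women are too few.

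Second, the study expects heart rate recordings from many more than 39 women, yet no sentence says which of them enter the heart rate analysis. The first 39, some other 39, or everyone with a usable recording would all be consistent with the text. A primary outcome should not leave that open until the data are in hand, particularly when the larger set would remove most of the power problem without enrolling anyone further.

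**Working it through.** **Inputs.** From Statistics: mean paired difference 1 minute, SD of the difference 3 minutes, two readings per woman, alpha 0.05, power 80%, paired t-test for continuous outcomes. Two assumptions are needed:

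- Sidedness is not stated for this calculation. The contraction calculation specifies a "two-sided type I error rate of not more than 5" percent, so two-sided is used here too.
- The ICC, meaning the correlation between the two readers' EUM-minus-Doppler differences for the same woman, is not given. It is varied from 0 to 1.

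**Formulas.** The mean of two readings has SD = 3 × √((1 + ICC)/2). The normal approximation gives n = SD² × (1.960 + 0.842)² / 1² = SD² × 7.85. Exact power uses the noncentral t with n − 1 degrees of freedom and noncentrality √n × 1/SD.

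**Reproducing the 39.** At ICC 0, SD² = 4.5 and n = 4.5 × 7.85 = 35.3, so 36 (38 by the t-test). At ICC 0.1, SD² = 4.95 and n = 38.9, so exactly 39. Solving backwards, 2 × 39/(9 × 7.85) − 1 = 0.10. With a single reading, n = 9 × 7.85 = 70.6, so 71 (73 by the t-test). The plan's figure is therefore reproduced, but only with two readings that are almost independent.

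**Power at 39 and women needed, by ICC (paired t, two-sided).**

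| ICC | SD of woman's mean | Power at 39 | n for 80% | n for 90% |
|---|---|---|---|---|
| 0 | 2.121 | 81.8% | 38 | 50 |
| 0.1 | 2.225 | 78.1% | 41 | 54 |
| 0.5 | 2.598 | 64.9% | 55 | 73 |
| 0.8 | 2.846 | 57.1% | 66 | 88 |
| 1 | 3.000 | 52.8% | 73 | 97 |

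Hand check at ICC 0.5 by the normal approximation: √39/2.598 − 1.960 = 2.404 − 1.960 = 0.444, which gives 67%. The t-test is slightly lower, at 65%.

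**Power if more women are analysed.** Only women recorded on Doppler inform this contrast, because the file holds a single monitor heart rate channel. The share on Doppler is not in the documents, so 50%, 70%, 90% and 100% of 110 women are shown as assumptions.

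| EUM–Doppler pairs | ICC 1 | ICC 0.5 | ICC 0 |
|---|---|---|---|
| 55 | 68.0% | 80% | 93.0% |
| 77 | 82.3% | 91.5% | 98.3% |
| 99 | 90.7% | 96.7% | 99.6% |
| 110 | 93.4% | 97.9% | 99.8% |

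With 220 pairs, power is at least 99.8% at any ICC.

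**Reading load.** 110 − 39 = 71 more women's tracings; 220 − 39 = 181 more.

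**The case against.** The strongest reply is that 39 is a requirement, not a limit. The list is introduced as the number of patients each aim needs, overlap between aims is expected, and the only women excluded from analysis are those monitored for under 30 minutes. On that reading, all usable heart rate pairs would be analysed anyway. The Statistics section also concedes that the study can detect only a substantial difference between EUM and Doppler.

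Much of this stands. A reader might infer that the plan discards the heart rate data of every woman after the 39th, or intends to pick 39 recordings. The documents do not say so, and the defect is silence about the analysis set. The silence still needs filling, and the general concession about power does not cover an unstated reader correlation.

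Three other stronger readings also fail:

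- **That the plan's own inputs give 53% power.** They do not. That is the ICC 1 case, where the second reading is worthless. The plan's inputs reproduce 39 at an ICC near 0 to 0.1.
- **That analysing everyone guarantees more than 90%.** This needs about 97 women on Doppler if the ICC may be as high as 1. The split is not given, and Device Description makes connecting the clinical monitor optional, so 110 or 220 pairs is an upper bound.
- **That a larger set makes reader correlation irrelevant.** At 55 pairs the range is still 68% to 93%. It narrows only as Doppler numbers rise.

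**Conclusion.** The point holds in this form: 39 women give about 80% power only under near-independence of the two readers, which the plan neither states nor supports, and the plan leaves open whether the other heart rate recordings it expects to collect will be analysed. Power at 39 ranges from 82% down to 53% over the full range of ICC. With 77 or more EUM–Doppler pairs it exceeds 80% at every ICC.

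These figures rest on the plan's 1 minute and SD of 3, read as the SD of one reader's difference, and on a two-sided test. If the calculation was meant as one-sided, 39 women would tolerate an ICC of about 0.3 (81% power) but would still fall to 76% at 0.5 and 66% at 1. The plan does not split alpha over its two primary outcomes. If it did so equally (0.025 each, an assumption), power at 110 pairs would be 88.8% to 99.6%. None of these figures applies to the scalp-electrode comparison, for which the plan assumes no effect size.

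**What to change.** In the Statistics list, replace the heart rate entry's 39 with wording such as: *all enrolled women with a complete 30-minute simultaneous EUM–Doppler recording, minimum 39*. Make the same change where Materials and Methods repeats the figure. Then:

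1. Analyse EUM–scalp-electrode pairs as a separate comparison. The Purpose section seeks superiority over Doppler but similar utility to the scalp electrode, and the one-minute effect is assumed for Doppler only, so the two kinds of pair should not be pooled.
2. Use one difference per woman, averaged over the two readers, in the paired t-test.
3. State the assumed reader correlation and whether the test is two-sided, then restate power for the expected number of Doppler pairs. If the assumed ICC is well above 0.1, the minimum of 39 must itself rise (55 at ICC 0.5, for example).

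No further women are needed. The cost is a few sentences in the plan and more reading by the same two obstetricians: about 70 more tracings each if 110 women are enrolled, and up to about 180 more if 220 are.

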#### Objectives:

Version 5.13; June 19, 2020

1. Compare the contraction tracings obtained using the EUM device vs. those obtained using the intrauterine pressure catheter vs. those obtained from external tocodynamometer among current obese patients (BMI greater than 30 kg/m^2) and nonobese patients using simultaneously obtained, 30 minute tracings with regards to the frequency of contractions, the duration of contractions, maximum height of the contractions, the total Montevideo units recorded, the timing of the contractions, and the amount of discontinuous tracings from the devices. Of the variables mentioned, the Montevideo units will only be comparable between the IUPC tracings and the EUM device.
2. Compare the fetal heart rate tracing obtained via the EUM device vs. external fetal Doppler vs. fetal scalp electrode (simultaneously obtained, 30 minute tracings will be compared) among obese patients and nonobese patients with regards to the amount of discontinuous/uninterpretable tracing, average fetal heart rate, baseline heart rate, the number accelerations, the number of decelerations, the timing of the accelerations, the timing of decelerations, the maximum fetal heart rate achieved during acceleration, the lowest fetal heart rate achieved during deceleration, and compare the degree of variability in the tracing.
3. Compare tracings of productive vs. non-productive contractions in patients presenting to triage to rule out labor (30 minutes of simultaneously obtained tracings of external tocodynamometer and EUM device will be compared) with regards to the frequency of contractions, the duration of contractions, maximum height of contractions, the timing of the contractions and the amount of discontinuous tracings from both devices, as well as changes in cervical exam on the basis of body mass index. Productive contractions are those that cause a change in cervical exam of 1 cm or more, any change in station or change in effacement of 50% or more.

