- Continuity in readings of fetal heart rate (as measured in the number of minutes without a readable tracing in a 30 minute sample tracing) between EUM and fetal scalp electrode and external fetal heart rate monitoring from the same patient
- Continuity in readings of contractions (as measured in the number of minutes without a readable tracing in a 30 minute sample tracing) between EUM, IUPC and external tocodynamometer from the same patient

Secondary Outcomes:

- Compare average frequency of contractions between the monitoring systems
- Compare duration of contraction between the monitoring systems
- Compare maximum height of the contraction between the monitoring systems
- Compare total Montevideo units obtained between the monitoring systems
- Compare the timing of the contraction between the monitoring systems
- Compare average fetal heart rate between the monitoring systems
- Compare baseline heart rate between the monitoring systems
- Compare the number accelerations between the monitoring systems
- Compare the number of decelerations between the monitoring systems
- Compare the timing of the accelerations between the monitoring systems
- Compare the timing of decelerations between the monitoring systems
- Compare the maximum fetal heart rate achieved during acceleration between the monitoring systems
- Compare the lowest fetal heart rate achieved during deceleration between the monitoring systems
- Compare the degree of variability in the tracing between the monitoring systems. Degree of variability will be defined as the correlation between the tracings. The tracings will be broken down into 4 minute intervals and defined as minimal, moderate or marked variability and compared with each other for accuracy and

Version 5.13; June 19, 2020

consistency. Most accurate will be the internal monitor in each case, i.e. fetal scalp electrode.

- Compare patient satisfaction between the monitoring systems

Inclusion criteria:

- 1) Maternal age >18 years old
- 2) Singleton pregnancy
- 3) Gestational age of 24 completed weeks or greater based on the estimated due date as calculated from last menstrual period or early ultrasound
- 4) Category I (reassuring) fetal heart rate tracing at time of enrollment

Exclusion criteria:

- 1) Fetal anomaly or chromosome defect
- 2) Allergy to silver
- 3) Woman with implanted electronic device of any kind
- 4) Irritated skin or open wound on the abdominal wall

Recruitment Mechanisms:

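### Acceleration and deceleration counts are compared over 30-minute tracings with no allowance for unequal readable time, so signal loss can appear as a difference in detection

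*Combined protocol and SAP*

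**What the plan says.** Objectives, item 2, compares EUM, Doppler and scalp electrode on tracings where "simultaneously obtained, 30 minute tracings will be compared", "with regards to the amount of discontinuous/uninterpretable tracing, average fetal heart rate, baseline heart rate, the number accelerations, the number of decelerations". The list goes on to the timing of events and to the highest and lowest rates reached during them. Secondary Outcomes repeats the items one by one, for example "Compare the number of decelerations between the monitoring systems". The Statistics section gives the list again ("In assessing fetal heart rate, we will compare average fetal heart rate, baseline heart rate, the number accelerations, the number of decelerations") and names one test for it: "A continuous outcome will be compared using a paired t-test".

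Continuity is the primary outcome, "as measured in the number of minutes without a readable tracing in a 30 minute sample tracing". The sample size for it rests on unequal loss: "Assuming the number of minutes of unreadable tracing for the EUM is less than the Doppler by one minute", and "the standard deviation of difference in minutes by the two devices is three minutes".

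Three provisions come near the problem, and none covers it:
- Statistics excludes women monitored for less than 30 minutes. This concerns the length of the recording, not gaps within it.
- Statistics expects missing data to be of little concern because each woman is her own control.
- Secondary Outcomes divides tracings into 4-minute intervals, but only to grade variability, and gives no rule for unreadable time.

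**The concern.** A count is the product of how often a device recognises an event and how long it was readable. The plan expects readable time to differ, then compares counts without holding it fixed. Two devices that agree on every event while both are readable will still give different counts if one loses more signal.

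The Purpose section aims to show accuracy: EUM similar to the internal devices and superior to the external ones. If EUM is more continuous than Doppler, it will tend to show more accelerations and decelerations, which could be read as better detection. If it is less continuous than the scalp electrode, it could be read as missing events. In either case the count partly repeats the primary outcome and is not separate evidence on accuracy.

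**Working it through.** **The plan's own figure.** For a paired mean, n = (SD × (1.960 + 0.842) / difference)². With SD 3 and difference 1 this gives 70.6 for one reading. Averaging two readings with correlation ρ multiplies it by (1 + ρ)/2: 35.3 (36 patients) at ρ = 0 and 38.9 (39 patients) at ρ = 0.1. By noncentral t at ρ = 0, n = 38, and power at 39 is 81.8%. The stated 39 is thus reproduced if the two readings are nearly independent. It confirms that a 1-minute difference with SD 3 is the plan's working assumption for heart rate at n = 39.

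**Model for counts.** Inputs from the plan: 30 minutes, a 1-minute difference in loss, n = 39, paired t-test (taken as two-sided, 0.05). Assumptions not in the documents:
- mean losses of 2 and 3 minutes, exponential and independent;
- Poisson events with mean λ = 3, 6 or 12 per 30 minutes;
- perfect detection in both devices whenever readable.

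Mean difference = λ × (3 − 2)/30 = λ/30, that is 3.3% of the true count.

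Variance of the difference = λ × [(2 + 3)/30 − 2 × 2 × 3/900] + λ² × (2² + 3²)/900 = 0.1533λ + 0.01444λ².

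The approximate false-positive rate uses the shift √39 × mean/SD against the t critical value 2.024.

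| λ | Mean difference | SD | Shift | Approximation | Simulation |
|---|---|---|---|---|---|
| 3 | 0.10 | 0.77 | 0.81 | 12% | about 12% |
| 6 | 0.20 | 1.20 | 1.04 | 16% | about 16% |
| 12 | 0.40 | 1.98 | 1.26 | 22% | about 23% |

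A repeat simulation of 6,000 studies per row gave 10%, 16% and 23%. Equal losses (2 and 2 minutes) gave about 5%.

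**A different loss model.** With the SD of the loss difference held at the plan's 3 minutes and 4 to 10 events, the rate at n = 39 was 15–24% for a 1-minute difference, 71–93% for 3 minutes and 97–100% for 5 minutes.

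**Holding readable time fixed.** Counts per readable minute gave 4.5–6.0% at n = 39. On time readable on both devices, this model gives identical counts by construction.

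**Maximum rate.** With event peaks of assumed SD 8 bpm, n = 39, the false-positive rate was 3–4% at 1 minute of extra loss, 15–17% at 3 minutes and 33–40% at 5 minutes.

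**The case against.** Several stronger readings are tempting, and the documents do not support them.

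- **That contractions are also compared as raw counts.** The plan compares their average frequency. If that is taken over readable time, the bias largely disappears. The fair criticism is that the denominator is not given.
- **That maximum and lowest heart rate are distorted under the plan's assumptions.** They are the extremes reached during accelerations and decelerations. At a 1-minute difference the check on the maximum found no inflation.
- **That most studies would show a false difference.** Rates of 70% and above need a difference in loss of about 3 minutes or more, which the plan does not assume.
- **That the authors will present signal loss as better detection.** The text does not say how the counts will be interpreted, and unreadable minutes will be reported beside them.
- **That whole-tracing counts are illegitimate.** The Purpose also covers clinical usefulness. What a device displays in 30 minutes of real use, gaps included, is a fair measure of that. Analysis of jointly readable time alone drops the difficult periods and can flatter every device.

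It is also true that the timing of events is compared separately, but no matching method is given, so this does not fill the gap. The plan mentions non-parametric analysis as well. A rank test on the same counts would face the same unequal exposure.

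What stands is that no rule covers gaps within the 30 minutes, and acceleration and deceleration counts are exposed to this at the plan's own effect size.

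**Conclusion.** The point holds for acceleration and deceleration counts used as evidence of accuracy. At the plan's 1-minute difference in loss and n = 39, devices with identical detection would differ significantly in about 12–23% of studies instead of 5%. The mean difference is 0.1 to 0.4 events, about 3% of the count. Larger differences in loss would give more.

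For contraction frequency the point is conditional on a 30-minute denominator. For maximum and lowest heart rate it matters only if the difference in loss is well above 1 minute.

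The event rates, the 2-minute baseline loss and the shape of the loss distribution are assumptions. The exponential model implies an SD of the loss difference of √13 = 3.6 minutes, slightly above the plan's 3, and the model fixed at 3 gave a similar 15–24% for 4 to 10 events. These are secondary outcomes, so the change is advisable but does not affect the primary analysis.

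**What to change.** In Statistics, after the list of heart rate and contraction comparisons, state that:

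1. The accuracy comparison of acceleration counts, deceleration counts and contraction frequency uses only time readable on both devices of the pair.
2. Within that time, events are matched to scalp-electrode or IUPC events using a time tolerance fixed in advance. The share matched and the number unmatched are reported.
3. Maximum and lowest fetal heart rate are compared only for events captured by both devices.
4. Events cut by the edge of a gap are left out of duration comparisons.
5. Whole-tracing counts are kept as a separate description of usefulness, and unreadable minutes remain the primary outcome.

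No new data or patients are needed: Device Description and the Option 2 setup show EUM and the conventional monitor written to one time-stamped file. The cost is slightly less tracing time per pair, a tolerance to be chosen in advance and a little more analysis work.

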#### Purpose:

We propose to perform a study to validate the accuracy and clinical usefulness of the EUM device by comparing it with simultaneous use of current methods (both external or internal devices) among obese patients and patients with normal body mass indexes (BMI). Our goal is to show that the EUM device is a noninvasive tool of similar utility to the fetal scalp electrode and the IUPC, and superior the traditionally used noninvasive devices (Doppler ultrasound and tocodynamometer).

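### For average and baseline fetal heart rate the plan names only a paired t-test of means, which cannot show how closely EUM agrees with the reference in individual women

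*Combined protocol and SAP*

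**What the plan says.** The Purpose section says the study is to "validate the accuracy and clinical usefulness of the EUM device" against simultaneous standard monitoring, and that the goal is to show a "noninvasive tool of similar utility to the fetal scalp electrode and the IUPC".

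The secondary outcomes in Materials and Methods include "Compare average fetal heart rate between the monitoring systems" and "Compare baseline heart rate between the monitoring systems". The Statistics section repeats the intention ("we will compare average fetal heart rate, baseline heart rate") and then gives the method in one sentence: "A continuous outcome will be compared using a paired t-test". The only other statement that could apply is general: "Routine parametric and non parametric statistical analysis will be performed".

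No limits of agreement, concordance measure, equivalence margin or acceptable error in bpm is given for these two outcomes. The nearest thing to an agreement analysis concerns another outcome: "Degree of variability will be defined as the correlation between the tracings". That item also classifies 4-minute intervals by variability and treats the FSE as the most accurate device.

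**The concern.** Average and baseline fetal heart rate are in bpm on every device, so the accuracy of an EUM value can be measured directly as its difference from the reference in the same woman. A paired t-test reduces those differences to their mean. Positive and negative errors cancel, and a larger spread of errors widens the standard error, so a less accurate device finds the test easier to pass. In the other direction, a precise device with a small constant offset can be declared different.

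The goal is similarity to the FSE, and a non-significant difference is not evidence of similarity. The Introduction says that no study of fetal heart rate with the EUM has yet been published, although it also cites accurate acquisition of fetal heart rate with abdominal sensors associated with the device. The fetal heart rate values from this study therefore matter, and the named analysis would leave their accuracy unreported.

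**Working it through.** **Inputs.** From the Statistics section: n = 39 for the fetal heart rate aim, significance level 0.05 (taken as two-sided), and the paired t-test. The documents give no SD for the between-device difference in bpm, so every SD in bpm below is an assumption and a range is shown.

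**The plan's own figure.** The 39 was derived for unreadable minutes, EUM against Doppler: difference 1 minute, SD 3 minutes, two readings per woman, 80% power. If the two readings are independent, the SD of their mean is 3/√2 = 2.12. The noncentral t then gives n = 38, with power 81.8% at n = 39. The figure reproduces to within one patient on that assumption. It was not sized for heart rate accuracy.

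**Test with no mean bias.** The paired t-test rejects 5% of the time at any SD, so it is non-significant 95% of the time. Limits of agreement are bias ± 1.96 × SD, and differences are taken as normal:

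| Assumed SD (bpm) | Limits of agreement (bpm) | Women more than 10 bpm off |
|---|---|---|
| 5 | ±9.8 | 5% |
| 10 | ±19.6 | 32% |
| 15 | ±29.4 | 50% |

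**Test with a 2 bpm bias, n = 39.** The noncentrality is 2 × √39 / SD, with 38 degrees of freedom. Rejection is 68% at SD 5, 23% at SD 10 and 13% at SD 15. The same bias is detected less often as individual error grows.

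**Test with a 1 bpm bias, n = 39.** The noncentrality is √39 / SD:

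| Assumed SD (bpm) | Noncentrality | Significant |
|---|---|---|
| 1.5 | 4.16 | 98% |
| 2 | 3.12 | 86% |
| 3 | 2.08 | 53% |
| 5 | 1.25 | 23% |

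At SD 1.5, about 95% of differences lie in 1 ± 1.96 × 1.5, that is from −1.9 to +3.9 bpm; about 2.3% exceed 4 bpm in size. The most precise device in this table is the one most often found to differ.

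**What limits of agreement would deliver.** The half-width of the 95% confidence interval for one limit is t(n−1) × SD × √(1/n + 1.96²/(2(n−1))). At SD 5 bpm:

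- n = 39: 2.024 × 5 × 0.276 = 2.8 bpm
- n = 20: 2.093 × 5 × 0.389 = 4.1 bpm
- n = 10: 2.262 × 5 × 0.560 = 6.3 bpm

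The 20 and 10 are illustrations. Internal monitors are used as clinically indicated (Materials and Methods), and the number of women who will have an FSE is not stated.

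**The case against.** The strongest reply is that these are 2 of some 15 secondary outcomes. The primary outcomes are continuity of the tracing, which the t-test on heart rate does not touch. Fetal heart rate accuracy is also approached elsewhere: variability is compared with the FSE as reference, and accelerations and decelerations are compared by number and timing. This stands, and it limits the point. A reader might infer that the whole accuracy aim goes unanswered; the documents do not support that. Only the accuracy of average and baseline heart rate values is left open.

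A reader might also infer that the investigators mean to claim accuracy from a non-significant t-test. No section says so. The risk is that the named analysis offers nothing else to go on.

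The general line on parametric and non-parametric analysis does not exclude an agreement analysis. But it names none, and a rank test would again address a shift in location. The correlation wording belongs to variability, and a correlation would miss a constant offset in any case.

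Two practical objections also stand. The recording file in Device Description, and the four signals in Option 2, have a single monitor heart rate channel, so it cannot be assumed that Doppler and FSE were both captured at the same time. And limits of agreement do not by themselves decide whether the EUM is similar enough, since the documents state no acceptable difference in bpm. They do report the quantity on which that judgement depends, which a p-value does not.

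**Conclusion.** The point holds for average and baseline fetal heart rate. The paired t-test tests mean bias only, so the heart rate value part of the accuracy aim is not answered. With no bias, the test at n = 39 is non-significant 95% of the time even when about a third of women are more than 10 bpm off (SD 10); a 1 bpm bias is significant in 98% down to 23% of studies as the SD goes from 1.5 to 5 bpm. The sizes rest on assumed SDs and normal differences. That the test becomes easier to pass as individual error grows, for a given non-zero bias, holds at any SD. Because these are secondary outcomes and the primary comparison is unaffected, this is a change that should be made, not one on which the study depends.

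**What to change.** In the Statistics section, make mean bias with 95% limits of agreement, each with a confidence interval, the main analysis of average and baseline fetal heart rate:

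- EUM against FSE in women whose connected monitor was an FSE, and EUM against Doppler in the others.
- Average rate computed on time readable on both devices.
- Woman as the cluster if there are several values per woman.
- The t-test kept only as the test of bias, with a statement that a non-significant result will not be read as agreement.
- Doppler against FSE only where both were actually recorded.

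The cost is a paragraph of plan wording and a little more analysis. EUM and connected-monitor heart rate are already stored side by side in one file, so this part needs no new data or patients. The downside is that limits against FSE will be imprecise if few women have one, and the report should give that number.
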